2.3.4 Differential splicing analysis

High quality data passing multiQC analysis will be retained for downstream differential splicing expression analysis. STAR version 2.7.1 software will be used to generate an index file mapped to the Human Genome Reference GRCh38 primary assembly and the GENCODE v34 annotation and generated using STAR's genome generate function with the argument - sjdbOverhang 149 and all other settings as default. Individual FASTQ files will be subsequently aligned to GRCh38 using STAR. Resultant unsorted BAM files will be sorted using Samtools version 1.16. Splicing junction files will be generated using RegTools version 0.5.2, and resultant files will be inputted into LeafCutter version 0.2.9 software for differential splicing analysis. Leafcutter only supports comparison of two groups and therefore differential splicing will be compared for each treatment group pre- and post-treatment and then between treatment and SoC. We will implement MAGIQ version 2.3 software for multigroup differential splicing analysis to compare each drug arm.

In summary, this transcriptomic analysis plan will interrogate our transcriptomic dataset on a pathway level as well as on an individual gene basis and enable a full characterisation of the molecular mechanisms and drivers of severe COVID-19 disease response to novel drugs.

2.4 Proteomics Analysis

Following quality control and quantitation of the 27 proteins (undertaken at the Medicines Evaluation Unit as part of the ACCORD trial) we will compare differences between the drugs and SoC arms. The dataset will be visualised using PCA plots with phenotype information overlaid to identify any unknown batches. If detected, batches will be corrected before or accounted for in the statistical modelling. Statistical analysis will be conducted to identify statistical differences between the different groups within this study (Each therapeutic compared to SoC and responders vs non-responders within each therapeutic arm). Shapiro wilk tests will be used but more likely we will use Mann-Witney U Tests between these groups. Following this we will also perform multiple testing corrections to the resulting p values.

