NIHR150393: Exploring and grouping COVID-19 pharmaceutical interventions to determine mechanisms of action and endotypes of response

This project is funded by the NIHR Efficacy and Mechanism Evaluation (EME) Programme (NIHR150393). The views expressed in this protocol are those of the author(s) and not necessarily those of the NIHR, NHS England or the Department of Health and Social Care

1 Research design

This research project is designed to identify the biological mechanisms through which novel COVID-19 drugs provide therapeutic benefit using data obtained from the ACCORD clinical trial(1). We will compare three novel therapeutics (Bemcentinib, Tozorakimab (previously known as MEDI3506) and Zilucoplan) to the Standard of Care (SoC) for severe COVID-19 patients using multiple data types (transcriptomics, proteomics, viral load, and pharmacokinetic drug levels). Each COVID-19 drug will be compared to the SoC of care individually before comparing the identified biological mechanisms comparatively to compare the mechanisms and conditions being modulated favourably by these drugs. Additionally, we will explore biological mechanisms and differences and relationships to effect size of clinical response as measured by time to improvement or discharge. This will better help us understand how the novel drugs work and how to select efficient treatments for a particular patient

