1.1 Study Population

The inclusion criteria for the ACCORD trial were:

Adults (>= 18 years) with SARS-CoV-2 infection confirmed by laboratory tests and/or point of care tests. Patients must be scored between Grade 3 (hospitalised – mild disease, no oxygen therapy) to Grade 5 (hospitalised - severe disease, non-invasive ventilation or high flow oxygen) on ACCORD's 9 point WHO ordinal scale from clinical improvement (OSCI) where Grade 0 is uninfected and 8 is death. Overall, in the ACCORD study 167 subjects were randomised, 14 subjects withdrew and 25 subjects died. In the additional Bemcentinib study, a further 115 were randomised – 60 to SoC and 55 to Bemcentinib in an identical study design.

1.2 Sampling.

Samples from patients were collected in line with the sample collection schedule below:

	Baseline								
Day	1	3	4	5	8	10	11	15	29
Biological sample type									
Blood (for RNA)	Х			Х		Х			
Blood (for serology)	Х							Х	
Blood (for protein)	Х			Х		Х			
Oropharyngeal swab (for viral load)	Х	Х		Х	Х		Х	Х	Х
Pharmacokinetic drug concentration									
Bemcentinib	Х		Xa		Х			Х	
Tozorakimab	Xb							Xc	
Zilucoplan	Х			Х		Х		Х	

Table showing the sample collection schedule for the ACCORD COVID-19 clinical trial.

Adapted from (1) to show only the samples collected to generate the datasets relevant to this current project. X = sample collected. All patients were sampled on day 1, which is considered baseline prior to the first dose of the assigned treatment arm or standard of care. Each drug had slightly different pharmacokinetic (PK) sampling regimes and were mostly collected predose. Where samples for PK were collected other than pre-dose, collection information is detailed below:

- ^a Sample collected pre-dose and 6 hours post-dose (Day 4).
- ^b Sample collected pre-dose and 15 minutes post-dose (Day 1).
- ^c Sample collected pre-dose and 15 minutes post-dose (Day 15).

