Missing data will be minimised, with outcomes collected after premature withdrawal of treatment. The primary clinical estimate will be analysed using a treatment policy strategy. If an OSS is missing on a particular study day, the unscheduled visits will be considered to see whether there was an unscheduled visit on that day. If so, the score from the unscheduled visit will be used. For the purposes of the primary analysis patients who died or were transferred will not be censored at day of death/transfer, time to clinical response will instead be censored as 29 days. Patients are considered to be in the study until Day 29 but a score of 8 will be imputed for the OSS for those who died from their date of death and for all subsequent visits. Moreover, if a patient withdraws and then dies and we have a record of their death then a score of 8 will be imputed from their date of death onwards for all analyses. For those who transferred, additional data post transfer has been collected and will be used. If a patient is discharged, has no Day 29 value but has a day 60 value they will be considered Alive for the mortality analysis and Last observation carried forward (LOCF) will be used to impute Day 29. If a patient has discharged and no additional data are available, then they are assumed alive at Day 29 and LOCF will be used to impute Day 29 value. If the OSS is missing on the date of discharge, this will be imputed to 2 (most conservative value possible for discharged patients). If the OSS is \geq 3 on the date of discharge, then the score will be imputed to 2. If a patient is subsequently readmitted and has ordinal scale data, then this data will be used. However, if data has not been entered upon readmission, then the patient will be considered a non-responder for the primary endpoint. Once they have been discharged then if OSS is missing it will be imputed as 2 for subsequent days. Reported ethnicity will be compared with ancestral ethnicity inferred using genetics data (Peddy software) and mapping of genotypes to gnomAD v2.1.1 data. Inferred (genetic ancestry) will be preferred over reported ancestry where discrepancies occur. Sex will be calculated counting genotypes on the X chromosome and be used preferentially where gender may not match biological sex.

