2.5 Other Factors

Viral Load, SARS-CoV-2 Serology, Pharmacokinetic drug concentration, patient demographics and clinical severity (baseline OSCI score) will be included in the pathway analysis model. These factors will be coded as numerical values and input as clinical traits for analysis of correlation with eigengene values of gene cluster modules within the WGCNA work stream.

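### The likely within-arm responder test for proteins ignores entry OSCI grade, so markers of entry severity could be reported as markers of response

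*Protocol*

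**What the plan says.** Section 1.1 sets the entry range: "Patients must be scored between Grade 3" (described there as "mild disease, no oxygen therapy") up to Grade 5, severe disease on non-invasive ventilation or high-flow oxygen. Section 1 links the biology to "effect size of clinical response as measured by time to improvement or discharge".

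Section 2.4 plans two sets of protein comparisons: each therapeutic against standard of care, and "responders vs non-responders within each therapeutic arm". On the test it says that "more likely we will use Mann-Witney U Tests between these groups", followed by a multiple-testing correction. It names no covariate or stratum for either comparison.

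Baseline control appears in three other places:

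- Section 2.2 compares baseline characteristics between treatment arms. It says the DESeq2 design will be updated to control for baseline factors and that protein models will use weighted baseline clinical data. The protein weights are not defined. The baseline list does not name OSCI grade, although it is open-ended and includes clinical observations.
- Section 2.3.1 repeats that baseline characteristics enter the DESeq2 design, and plans a responder comparison for each drug.
- Section 2.5 is the only place where baseline grade is named for an analysis: "clinical severity (baseline OSCI score) will be included in the pathway analysis model". It is used there as a numerical trait correlated with WGCNA module eigengenes.

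**The concern.** Entry grade can plausibly affect both sides of the responder comparison. Sicker patients may be more or less likely to respond by Day 29, and cytokine levels may differ with severity. If both hold, responders and non-responders within an arm differ in entry grade. An unadjusted rank test then picks up that difference even for a protein unrelated to response among patients of the same grade.

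Randomisation does not protect this contrast, because responder status is observed after entry and not allocated. The multiple-testing correction limits chance findings and does nothing about confounding. What is at stake is the project's stated product, endotypes of response that help choose a treatment for a patient. A severity marker could be put forward as one.

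**Working it through.** The protocol states no sample size, power or effect size for the responder contrasts, so there is no figure to reproduce. The check has three parts.

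**1. The sections side by side.** Section 2.2 promises weighted baseline data in the protein models. Section 2.4 names as the likely test a Mann-Whitney U test, whose only inputs are the two groups' values. The two do not fit together as written. The baseline comparison in 2.2 is between arms, and weights built for that purpose would leave responders and non-responders within one arm unbalanced. The eigengene correlation in 2.5 adjusts no responder contrast.

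**2. Size of a spurious gap.** The grade mix, the response rates by grade and the protein shift per grade are all assumptions; the protocol gives none of them. For grade g with share p(g) and response rate r(g):

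- mean grade of responders = Σ g·p(g)·r(g) / Σ p(g)·r(g)
- mean grade of non-responders = Σ g·p(g)·(1−r(g)) / Σ p(g)·(1−r(g))
- spurious gap = difference in mean grade × 0.5 SD per grade (assumed)

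Main case, mix 30/40/30% and response 90/80/60% at Grades 3/4/5:

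- Responders: shares 0.27/0.32/0.18, total 0.77; mean = (0.81 + 1.28 + 0.90)/0.77 = 3.88. Grade 5 makes up 0.18/0.77 = 23%.
- Non-responders: shares 0.03/0.08/0.12, total 0.23; mean = (0.09 + 0.32 + 0.60)/0.23 = 4.39. Grade 5 makes up 0.12/0.23 = 52%.
- Difference 0.51 grade; gap 0.51 × 0.5 = 0.25 SD.

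| Mix, Grades 3/4/5 | Response, Grades 3/4/5 | Mean grade, non-responders | Mean grade, responders | Gap |
|---|---|---|---|---|
| 20/60/20% | 90/85/70% | 0.72/0.17 = 4.24 | 3.28/0.83 = 3.95 | 0.14 SD |
| 30/40/30% | 90/80/60% | 4.39 | 3.88 | 0.25 SD |
| 30/40/30% | 95/80/50% | 1.115/0.245 = 4.55 | 2.885/0.755 = 3.82 | 0.36 SD |
| any | equal | same | same | 0 |

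**3. False-positive rate.** This was simulated with 2,000 trials per scenario, two-sided 0.05, and no link between protein and response within grade. Assumptions: grade mix 20/50/30%, protein shift 0.25 to 1.0 SD per grade, and 55 patients. The figure of 55 is the number randomised to Bemcentinib in the additional study; the number with protein data is not given.

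| Response, Grades 3/4/5 | Unstratified Mann-Whitney |
|---|---|
| 80/80/80% | 4.1 to 4.8% |
| 90/80/70% | 5.3 to 9.9% |
| 70/80/90% | 5.5 to 11.1% |
| 90/75/50% | 6.1 to 26.2% |

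With 30 patients the inflation is smaller, reaching 15.6% in the steepest case. A van Elteren test stratified by entry grade stayed between 3.4% and 5.3% in every scenario at both sizes.

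**The case against.** The best defence is that the protocol does promise baseline control, and that choosing covariates is ordinary SAP content. For gene expression this largely stands. Sections 2.2 and 2.3.1 both commit to baseline terms in DESeq2, and the open list in 2.2 could include entry grade. A reader might infer that the DESeq2 responder contrast leaves grade out. The protocol does not say so; it leaves the matter open. For proteins the defence is weaker, because 2.4 names a likely test that has no place for the promised baseline data.

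A second tempting reading is that response means a different clinical state at every entry grade, so that the labels themselves are unequal. The documents do not support this. No section says how many points count as improvement. The only rule that names a non-responder is in section 2.1, for a readmitted patient without data: "then the patient will be considered a non-responder for the primary endpoint". Take response as a fall of k points or discharge (score 2 or lower). The highest score that counts for entry Grades 3/4/5 is then 2/3/4 if k = 1, 2/2/3 if k = 2 and 2/2/2 if k = 3. The bar differs at every grade only under a one-point rule. The gaps calculated above do not measure unequal labels either. They are ordinary confounding by prognosis and would arise under any response definition.

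It is also fair to object that the size is unknown. The SD range assumes response falls with grade. If response rises with grade, the gap changes sign; if it is flat, there is none.

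**Conclusion.** The point holds for the protein analysis. Followed as written, section 2.4 would compare responders with non-responders without regard to entry grade, contrary to what section 2.2 promises. The result could be confounded by entry severity. Whether it will be depends on two relations that the protocol does not give: response rate by grade, and protein level by grade. If both are present, a spurious gap of roughly 0.14 to 0.36 SD is what the assumed falling-response scenarios yield at 0.5 SD per grade. If response rates are equal across grades it is nil.

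For the DESeq2 responder contrast the finding is milder: control is promised, and baseline OSCI simply needs naming.

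A sensitivity analysis that redefines response as reaching a score of 2 or lower might seem to solve the problem. It would not remove the confounding and could enlarge it, since the criterion can only keep or lower response among Grade 5 entrants while leaving Grade 3 unchanged. For example, with the 30/40/30% mix and assumed rates of 90/75/45%, mean grades are 1.315/0.295 = 4.46 in non-responders and 2.685/0.705 = 3.81 in responders. The gap is 0.65 grade, or about 0.32 SD, against 0.25 SD in the main case.

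**What to change.** - **Section 2.4:** replace the unadjusted Mann-Whitney test for the responder contrast with one stratified by, or adjusted for, baseline OSCI grade (3, 4, 5). A van Elteren test would do, as would a rank or linear model with grade as a factor. This also reconciles 2.4 with 2.2.
- **Section 2.3.1:** name baseline OSCI grade as a fixed term in the DESeq2 design for the responder contrasts, and in the limma design where pathway scores are compared in the same way.

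Entry grade is already collected, so no new data are needed. The cost is one or two degrees of freedom and slightly less power in small arms. In a stratified test, a grade in which every patient responds, or none does, contributes nothing.

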1.2.1.2 Proteomic dataset (Luminex)

A Bio-Plex Pro Assay kit was utilised to assess the concentrations of cytokines, chemokines and growth factors in the study population from samples taken on days 1 (pre-treatment), 5 and 10 of admission. The 27 cytokines, chemokines and growth factors measured are: IL-1 β , IL-1ra, IL-2, IL-4, IL-5, IL-6, IL-7, CXCL8/IL-8, IL-9, IL-10, IL-12p70, IL-13, IL-15, IL-17A, Eotaxin, Basic FGF, G-CSF, GM-CSF, IFN- γ , IP-10, CCL2/MCP1, CCL3/MIP-1 α , CCL4/MIP-1 β , PDGF-BB, CCL5/RANTES, TNF- α and VEGF. Following analysis of each batch, 27 reports (one for each analyte) containing the assay results (in pg/ml) were generated using the xPONENT for MagPix software and saved within the study specific electronic file. A CSV file will be generated and exported for further analysis.

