2.2 Comparison and confounding of baseline clinical characteristics

Baseline clinical characteristics, including age, sex, ethnicity, significant comorbidities, laboratory results and clinical observations will be recorded, assessed and compared between patients in different treatment arms using R (v 4.1.2). Patient statistics tables will be calculated to test for any significant confounding variables between blinded groups. Principal component analysis of normalised expression values will be correlated with axes of variation e.g. ethnicity, to identify clusters affecting gene expression.

Differential gene expression analysis will control for baseline factors that may skew analysis by updating the statistic model design in DESeq2. Differential splicing analysis will be subject to weighting by multinomial covariate-balanced propensity scores to control for baseline confounding factors, as implemented by the R package Weightlt version 0.12.0, using the "just-identified" approach. Proteomics models will incorporate weighted baseline clinical data to avoid bias.

2.3 Transcriptomic analysis

The focus of this study will be the analysis of the transcriptomics dataset comprising patient data taken at three time points for three novel drugs and the SoC trial arm. The RNA-Sequencing samples have been generated and the raw FASTQC data have been downloaded from the ACCORD clinical trials platform. These data have been subject to quality control as previously described in the methods section. To avoid any unintentional bias, the groups will be blinded so that the bioinformatician will not know which patient group or SoC arm is which. The novel drug and SoC arms will be given a random identifier such as A, B, C or D for the duration of this analysis.

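### The rank test expected for the protein comparisons cannot carry the baseline adjustment that section 2.2 promises, and the Day 1 protein level has no stated role

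*Protocol*

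**What the plan says.** Section 2.2 of the protocol makes a commitment for the protein data: "Proteomics models will incorporate weighted baseline clinical data to avoid bias". The baseline data it has in mind are listed in the same section: "Baseline clinical characteristics, including age, sex, ethnicity, significant comorbidities, laboratory results and clinical observations will be recorded". The Day 1 protein level is not named there.

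Section 2.4 is where the 27 proteins are compared between groups. The comparisons are: "Each therapeutic compared to SoC and responders vs non-responders within each therapeutic arm". The method is: "Shapiro wilk tests will be used but more likely we will use Mann-Witney U Tests between these groups". Multiple-testing correction follows. On batches the section says: "If detected, batches will be corrected before or accounted for in the statistical modelling". It names no regression model, covariate or weight.

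Section 1.2.1.2 states that the proteins were measured "from samples taken on days 1 (pre-treatment), 5 and 10 of admission". Section 2.4 does not say which day is tested, or whether the tested value is the raw concentration or a change from Day 1.

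**The concern.** Sections 2.2 and 2.4 do not fit together. One promises adjustment; the other expects a two-group rank test that has no place for it. The other data streams are told how adjustment will be done: gene expression through the DESeq2 design, splicing through propensity-score weights. The protein stream has a promise without a mechanism.

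The stakes differ between the two comparisons. Drug versus SoC is randomised, so an unadjusted test is valid but less precise than it could be. Responders versus non-responders within an arm is not randomised. The two groups may already differ on Day 1, and an unadjusted test at follow-up can present that difference as part of the drug response, which is the question the project asks.

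**Working it through.** **Consistency check.** Section 2.2 requires weights or covariates in the protein analysis. The standard Mann-Whitney statistic depends only on the ranks of one variable in two groups. An analyst who follows section 2.4 as written therefore cannot meet section 2.2. This needs no arithmetic.

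**Size of the precision loss.** The protocol gives no power, alpha or effect size for proteins, so there is no figure to reproduce. What follows is an illustration of Day 1 protein adjustment. It does not measure the loss from leaving out the clinical covariates of section 2.2.

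Inputs:
- From section 1.1: 60 SoC and 55 Bemcentinib randomised in the additional study.
- Assumed: log-normal concentrations, effect 0.5 SD on the log scale, two-sided 0.05 for one protein before multiplicity correction, correlation ρ between Day 1 and follow-up of 0.3 to 0.7, every randomised patient sampled; and 35 per arm as a smaller case.

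Formula: power ≈ Φ(0.5/SE − 1.96), with SE = √[v(1/n₁ + 1/n₂)]. For Mann-Whitney on the follow-up value v = 1/0.955. For ANCOVA on Day 1, v = 1 − ρ².

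At 60 versus 55, 1/60 + 1/55 = 0.03485:
- Mann-Whitney: SE = √(0.03485/0.955) = 0.191; 0.5/0.191 = 2.62; power about 0.75.
- ANCOVA, ρ = 0.3: SE = √(0.91 × 0.03485) = 0.178; power 0.80.
- ANCOVA, ρ = 0.5: SE = √(0.75 × 0.03485) = 0.162; power 0.87.
- ANCOVA, ρ = 0.7: SE = √(0.51 × 0.03485) = 0.133; power 0.96.

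At 35 per arm, simulation with 4,000 runs per setting gives about 52% for Mann-Whitney, and 65% (ρ = 0.5) or 81% (ρ = 0.7) for ANCOVA. The formula gives 53%, 68% and 83%; it is slightly optimistic in small samples. At ρ = 0.3 the gain is small, from 52% to about 57%. With no effect and no imbalance, all methods reject about 5% of the time.

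**Non-randomised contrast.** Suppose the groups differ by 0.5 SD on Day 1 and there is no further difference at follow-up given Day 1. Simulated rejection rates at an assumed 35 per group:

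| Day 1 correlation | Mann-Whitney, follow-up value | Mann-Whitney, change | Day 1-adjusted model |
|---|---|---|---|
| 0.3 | 8% | 23% | about 5% |
| 0.5 | 17% | 17% | about 5% |
| 0.7 | 28% | 13% | about 5% |

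Testing change scores therefore does not remove the problem.

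**The case against.** Several points on the other side are fair.

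- The protocol says Mann-Whitney is more likely, not fixed. Weighted and covariate-adjusted rank methods exist. This stands, but section 2.4 names none of them, and the expected choice conflicts with section 2.2.
- A reader might infer that the plan ignores Day 1 and treats Days 5 and 10 as unrelated. The text does not say so; it is silent on the day and on the value tested. A rank test on change from Day 1 would use Day 1, and at 60 versus 55 it reaches 0.92 power against 0.96 for ANCOVA when ρ = 0.7. At ρ = 0.5 it reaches only 0.75 against 0.87. What can be said is that Day 1 has no stated role. Since section 2.2 speaks of clinical data, this is a weakness beside the contradiction and not part of it.
- A reader might infer that batch handling fails too. It does not: correction before testing is one of the two permitted routes and works with a rank test.
- A reader might infer bias in drug versus SoC. Randomisation protects those contrasts. At 60 versus 55 a chance Day 1 difference has standard error √0.03485 = 0.19 SD, so absolute differences of at least 0.3 or 0.5 SD occur with probability of only about 0.11 or 0.007.
- A reader might infer damage to the integration of transcripts and proteins. Sections 2.6 to 2.6.4 work on individual-level expression data and not on these p-values, so that harm is not supported.
- Section 2.2 also plans baseline significance tests: "Patient statistics tables will be calculated to test for any significant confounding variables between blinded groups". That concerns all data streams and is a separate matter; here it only bears on how covariates are chosen.

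Finally, the project is exploratory and its stated focus is transcriptomics. That lowers the severity but leaves the conflict in place.

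**Conclusion.** The point holds as a conflict between sections 2.2 and 2.4: the expected protein test cannot deliver the stated adjustment. In the randomised contrasts the illustrated cost is precision. It is 13 to 29 percentage points of power at 35 per arm (65 − 52 and 81 − 52, for ρ = 0.5 and 0.7) and about 5 to 21 points at 60 versus 55 (80 − 75 and 96 − 75, for ρ = 0.3 and 0.7). These figures rest on the assumed effect, correlations and evaluable numbers and apply to a single protein at 0.05; multiplicity correction would lower the power of both methods. In the responder comparison there is also a risk of confounding, whose size depends on how far the groups differ on Day 1, which the protocol does not give. The severity is should-fix: the work is exploratory and no protein-level power is claimed.

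**What to change.** Reconcile sections 2.2 and 2.4 by replacing the Shapiro-Wilk/Mann-Whitney rule with one prespecified model per protein:

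- Outcome: log concentration at Days 5 and 10, with patient as random effect.
- Covariates: log Day 1 concentration, day, age, sex and baseline OSCI, fixed in advance and not selected by baseline significance tests.
- Drug versus SoC: arm and arm-by-day.
- Responders versus non-responders within an arm: responder status and responder-by-day, reported as an association because the groups are not randomised.
- Batch: corrected beforehand or entered as a factor.
- Sensitivity analysis: rank-based ANCOVA.
- Multiple-testing correction: kept.

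Section 2.2 should then describe the protein adjustment in these terms. No new samples are needed. The cost is rewording, some extra analysis work, and a stated rule for patients without a Day 1 protein value.
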